NCT#: NCT04138017

Document Date: 19 August 2021

PROTOCOL

Background

1. Provide the scientific background, rationale and relevance of this project.

INSTRUCTIONS

- This should include a referenced systematic evidenced-based review when possible.
- If this study involves qualitative research explain the major constructs of your study.
- Do not state in this section what you plan to do in this study. This information should be entered later under "What will be done in this protocol?"
- Do not include the bibliography in this section.
- For studies submitted under the Expedited review criteria, this section need not be more than a few paragraphs.
- For those studies where data will be analyzed collaboratively by multiple sites doing
 a similar study for which there is no common protocol (Collaborative Site Analysis
 Study) include a description of the common scientific goals/ procedures/data points.
- If this is a FIVE YEAR UPDATE make sure the information throughout the protocol includes the most current information.

Answer/Response: Arthrodesis procedures for the ankle and hindfoot are performed to correct deformity and treat end-stage arthritis. However, recent literature has demonstrated that 10-40% of ankle fusions result in non-union (1,2). For triple arthrodesis (talonavicular, subtalar, and calcaneocuboid joints), published rates of non-union range from 0-10% (3). However, recent literature from our institution demonstrated significantly higher rates of non-union when calcaneo-cuboid sparing hindfoot arthrodesis was performed (4). Given that not every non-union results in a revision surgery, it is likely that the published rates of non-union underestimate the true rate of this complication. Due to the extended period of convalescence after these major arthrodesis procedures, non-union is a devastating outcome. Loss of mobility, loss of income from employment, and increased health care expense and patient risk for a second procedure contribute to the economic and emotional impact of non-union upon these patients.

Currently, many alternatives to autograft harvest are being evaluated for foot and ankle arthrodesis. Given the known complications of autograft harvest (incision pain, nerve injury, infection, 1), alternatives which possess osteogenic, osteoconductive, and osteoinductive properties are an attractive option when supplementing complex hindfoot arthrodesis procedures. A recent publication demonstrated a superior fusion rate for purified recombinant human platelet-derived growth factor BB homodimer (rhPDGF-BB) when compared to autograft (5). However, arthrodesis rates, as confirmed on CT scan, were only 84% and 65% respectively.

ViviGen (Depuy Synthes) is a cellular bone matrix, which includes viable osteoblasts within a corticocancellous and demineralized bone carrier, represents a unique alternative to autograft or existing products which utilize mesenchymal stem cells. ViviGen Cellular Bone Matrix is a Human Cells, Tissues, and Cellular and Tissue-based Product (HCT/P) as defined by the U.S.

Version Date: 08/19/2021 Page Number: 1 of 10

Food and Drug Administration in 21 CFR 1271.3(d). ViviGen Cellular Bone Matrix is processed from donated human tissue, resulting from the generous gift of an individual or his/her family. This product is classified as a **biologic** by the FDA. Given our encouraging early data using Vivigen for complex and revision arthrodesis procedures in the foot and ankle, our Foot and Ankle Clinical research group at the University of Virginia wishes to conduct a prospective study to evaluate 1-Year implant survivorship in subjects who receive the implant when used for primary ankle or hindfoot arthrodesis procedures as part of their clinical care.

Our study would prospectively follow primary ankle or hindfoot arthrodesis procedures. Ankle arthrodesis, tibiotalocalcaneal arthrodesis, subtalar and triple arthrodesis procedures would be included in this cohort, and CT scan would be utilized to demonstrate successful arthrodesis (defined by >50% fusion). Patient outcome measures including Foot and Ankle Activity Measures, AOFAS hindfoot score, and VAS pain scores would be recorded pre-operatively and for 1 year post operatively.

The purpose of this study is to examine 1-year outcomes. ViviGen Cellular Bone Matrix is being given as part of clinical care. The only research procedures are questionnaires and blood draw for Vitamin D.

Objectives/Hypothesis

INSTRUCTIONS:

If this study involves biomedical research clearly state the objectives and hypotheses and clearly define the primary and any secondary outcome measures. If this study involves qualitative research clearly state your research hypothesis or question.

This section should not include information already included in other sections such as background information or information from the procedures section.

Answer/Response: To evaluate 1-Year implant survivorship in subjects who receive the implant when used for primary ankle or hindfoot arthrodesis procedures.

Study Design: Biomedical

1. Will controls be used?

Answer/Response: No.

► IF YES, explain the kind of controls to be used.

Answer/Response:

2. What is the study design?

Example: case series, case control study, cohort study, randomized control study, single-blind, double-blind, met-analysis, systematic reviews, other. You may also view the IRB-HSR Learning Shot on this topic to help you answer this question. (http://www.virginia.edu/vpr/irb/learningshots/Writing protocol June09/player.html

Answer/Response: This is a post-market, prospective, non-randomized, PI initiated, open-label clinical evaluation of the implant for use in primary ankle or hindfoot

Version Date: 08/19/2021 Page Number: 2 of 10

arthrodesis. Data will be collected at specific time points and entered into case report forms (CRFs) based on the information contained in the patient medical records.

3. Does the study involve a placebo?

Answer/Response: No.

▶ IF YES, provide a justification for the use of a placebo

Answer/Response:

Human Participants

 Ages:
 18-80

 Sex:
 All

 Race:
 All

Subjects- see below

INSTRUCTIONS: For question 1-4 below insert an exact #. Ranges or OPEN is not allowed. This # should be the maximum # you expect to need to enroll (i.e. sign consent) If you are only collecting specimens the number of participants should equate to the # of specimens you need. If you are collecting only data from a chart review the number should designate the number of subjects whose medical records you plan to review. Age/ Sex/Race criteria should designate the demographics of participants from whom you will obtain the specimen/data.

1. Provide target # of subjects (at all sites) needed to complete protocol.

INSTRUCTIONS: If this is NOT a database protocol, this number should be the same as the number of subjects needed to obtain statistically significant results.

Answer/Response: 15

2. Describe expected rate of screen failure/ dropouts/withdrawals from all sites.

Answer/Response: 10%.

3. How many subjects will be enrolled at all sites?

INSTRUCTIONS: This number must be the same or higher than the # from question # 1 in order to account for the # of screen failures, dropouts, withdrawals described in question # 2.

Answer/Response: 18.

4. How many subjects will sign a consent form under this UVa protocol?

INSTRUCTIONS: If the protocol does not have a consent form- the number listed here should reflect such things as the number of subjects from whom specimens will be obtained, the number of charts to be reviewed etc.

Answer/Response: 18.

Version Date: 08/19/2021 Page Number: 3 of 10

Inclusion/Exclusion Criteria

INSTRUCTIONS:

- The inclusion and exclusion criteria should be written in bullet format.
- This item applicable if the study will require consent (verbal or written). Unless there is a scientific reason for not recruiting a certain type of vulnerable population(e.g. not enrolling fetuses, neonates or children in a study regarding Alzheimer's) list the following vulnerable populations under either Inclusion or Exclusion criteria below: pregnant women, fetuses, neonates, children, prisoners, cognitively impaired, educational or economically disadvantage, non- English speaking subjects.
- If you will not enroll subjects who do not speak English because certain procedures cannot be carried out if the subject does not speak English (e.g. a survey is not validated in other languages) insert the following as an Inclusion Criteria: Willingness and ability to comply with scheduled visits and study procedures.
- If this is a collection of only retrospective* specimens or data, the inclusion criteria must include a start and stop date for when specimens/ data will be collected.
- The stop date must be prior to the version date of this protocol.
- *Retrospective: all specimens are in a lab at the time this protocol is approved by the IRB. All data exists in medical records or records from previous studies at the time this protocol is approved by the IRB.

1. List the criteria for inclusion

Answer/Response:

- Patient with prescribed standard of care unilateral hindfoot ankle arthrodesis
 procedure who will receive the ViviGen® Cellular Bone Matrix as part of their clinical
 care
- Age 18-80
- Willing to complete all follow up evaluations

2. List the criteria for exclusion

Answer/Response:

- Prior infection at site of planned arthrodesis
- Inability to maintain non-weight bearing status
- Bone defect requiring more than 10 cc of bone graft material
- A Vitamin D level of < 30ng/mL pre-operatively
 - -Testing can be completed up to 1 week prior to surgery
- Inadequate bone stock to allow for rigid internal fixation.
- BMI greater than 40
- Pregnancy per review of current lab results in medical record of childbearing females.
- Cognitive inability to provide informed consent
- Tobacco or nicotine use 6-weeks prior to surgery
- Hemoglobin A1C >8.0
- Not-English speaking individuals

Version Date: 08/19/2021 Page Number: 4 of 10

3. List any restrictions on use of other drugs or treatments.

Answer/Response: N/A.

Statistical Considerations

1. Is stratification/randomization involved?

Answer/Response: No.

► IF YES, describe the stratification/ randomization scheme.

INSTRUCTIONS:

The stratification factors and/or the randomization plan should be identified. If there is no randomization component or important patient characteristics that will be used in treatment allocation or data analysis, a statement to this effect should be included.

Stratification factors: These are pretreatment patient characteristics which could be balanced across treatment arms by design or may be used to determine starting dose or treatment allocation.

If randomization is going to be used, the details of the randomization plan should be described.

The description should include:

- -- the method and timing of randomization
- --the type of randomization scheme that will be used in the study
- --whether or not the randomization masked/blinded/if so, then to whom is it masked/blinded
- --who has access to the randomization scheme

Answer/Response: NA

▶ IF YES, who will generate the randomization scheme?

Sponsor			
UVa Sta	itistician.	Insert name	Answer/Response
UVa Investigational Drug Service (IDS)			
Other:	Specify	Answer/Respo	onse:

2. What are the statistical considerations for the protocol?

The objectives section and the statistical section should correspond, and any objective for which analysis is unfeasible should be deleted. Also, the estimates and non-statistical assumptions of the statistical section should be supported by discussion in the background section.

The answer to this question should include:

--Study Design/Endpoints

Version Date: 08/19/2021 Page Number: 5 of 10

- --Recap of study objectives and endpoint definitions. An assessment of how study objectives will be assessed by identifying & defining which endpoints will be used to assess each component of the study objectives.
- --The study design should include contingencies for early stopping, interim analyses, stratification factors (If applicable), and any characteristics to be incorporated in analyses.
- --The power/precision of the study to address the major study endpoint(s), the assumptions involved in the determination of power/precision.
- --If statistical hypothesis testing is included then specify the null and alternative hypotheses, the test statistic, and the type I and II error rates
- --If precision of an estimate, then provide a definition for precision
- --If other, then specify

Answer/Response: We will compare primary outcome measures as a binary outcome using chisquare or Fisher exact analyses using existing failure rates as a historical control. We will use standard parametric statistical analyses to determine change from pre-post surgery and referencing historical control data obtained from the literature. Multivariate statistical modelling will be considered for potential sources of confound if appropriate.

3. Provide a justification for the sample size used in this protocol.

Include the anticipated accrual rate, the accrual goal for the study, including accrual goals by strata if appropriate, adjustments for drop-outs etc. and study duration.

Answer/Response: ViviGen is already an FDA approved biologic, therefore a large sample size is not needed.

4. What is your plan for primary variable analysis?

Include a sketch of the analysis to assess primary study objectives.

Answer/Response: Radiographic evidence of successful arthrodesis confirmed on CT (defined by >50% fusion)

5. What is your plan for secondary variable analysis?

Include the following:

- -- A sketch of the analysis to assess secondary study objectives.
- --For phase III studies, the power/precision of the study to address the secondary objective(s).

Answer/Response:

- Clinical & Radiographic evidence of failure (obvious non-union or hardware failure)
- Patient reported outcomes scores
- Vitamin D levels

6. Have you been working with a statistician in designing this protocol?

Answer/Response: No.

IF YES, what is their name?

Answer/Response:

Version Date: 08/19/2021 Page Number: 6 of 10

7. Will data from multiple sites be combined during analysis?

Answer/Response: No.

INSTRUCTIONS: IF YES, answer the following questions

7(a). Does the study involve randomization?

Answer/Response:

IF YES, will randomization be done at each site or among sites?

Answer/Response:

7(b). Has the sample size calculation considered the variation among sites?

Answer/Response:

7(c). When combining the data from multiple sites to assess the study results, is the effect of the treatment to be tested (or the association to be tested) assumed to be the same across sites or vary among sites? What is the modelling strategy?

Answer/Response:

7(d). Is there a common protocol used in all sites?

Answer/Response:

IF NO, how will differences among sites, such as those related to the implementation, inclusion criteria, patient characteristics, or other sites characteristics, be considered to assess the study results?

Answer/Response:

Study Procedures-Biomedical Research

1. What will be done in this protocol?

INSTRUCTIONS:

This should include everything that will be done as part of this protocol. Do not repeat information that is included in other sections such as Background or Hypothesis sections.

This section should include an indication of which research interventions if any offer a prospect for direct benefit and which interventions (invasive measurements, collection of blood, tissue, data, surveys, etc.) are being done solely to answer a research question and generate generalizable knowledge. If the interventions done solely for research purposes are associated with greater than minimal risk they need to be justified. Describe and justify any control and experimental arm and include method, dose, and duration of drug administration. Reference any claim of clinical equipoise if applicable.

If you are obtaining specimens or data, provide information regarding the type of specimen/data, amount of specimen needed and how the specimen/data will be obtained and what analysis will be done with the specimen/data.

Special note for studies with waiver of consent/waiver of documentation of consent: Include a statement regarding how subjects will be recruited. For other studies this information is captured in Recruitment does not need to be duplicated in this section.

Version Date: 08/19/2021 Page Number: 7 of 10

Answer/Response: All study visits will be performed when the patient comes in for clinical care.

VISIT 1: SCREENING/BASELINE (will add about 45 minutes to your visit):

If you decide to be in this study, you will read and sign this consent form before any study related procedures take place. You will meet with the study doctor to determine if you are eligible and it is safe for you to participate in the study. This will include the following:

The following procedures will be done as **part of your clinical care** and recorded for research purposes in preparation for your arthrodesis surgery.

- Reviewing your medical history, including your smoking history and current alcohol use.
- Physical exam as well as your weight and height
- Review your current medications.
- If you are a female and able to have children, your physician will ask if you are pregnant and may perform a urine or serum pregnancy test to confirm that you are not pregnant.
- If you are not already currently taking Vitamin D supplements, it will be prescribed to you by your surgeon as part of your standard of care before surgery

The following procedures/assessment will be done solely for research purposes:

- Complete study questionnaires that will ask you about your level of pain, your daily activities, physical function, and quality of life. The questionnaires will take about 20 minutes to complete.
- Laboratory testing including collection of blood samples (1 ½ teaspoons)
 - o Your blood will be analyzed to assess your Vitamin D levels

VISIT 2: SURGERY (as part of your clinical care) (will last about 2 ½ hours):

The following procedures will be done as **part of your clinical care** in preparation for your arthrodesis surgery. The results will also be recorded for research purposes:

- Recording of admission and surgical information from your medical chart
- Primary ankle or hindfoot arthrodesis using the ViviGen graft
- Surgical images of the hindfoot/ankle (intra-operative fluoroscopy and post-operative x-ray)

FOLLOW-UP (each visit will add about 45 minutes to your visit): VISIT 3 –2 Weeks Post Surgery

The following procedures will be done as **part of your clinical care.** The results will be recorded for research purposes:

- Wound Check
- Physical assessment of the hindfoot/ankle, including vital signs

VISIT 4 - 6 Weeks Post Surgery

Version Date: 08/19/2021 Page Number: 8 of 10

The following procedure will be done as **part of your clinical care.** The results will be recorded for research purposes:

- Physical assessment of the hindfoot/ankle, including vital signs
- X-rays of the hindfoot/ankle

VISITS 5, 6, and 7 –3 months, 6 months and 12 months Post-Surgery

The following procedures will be done as **part of your clinical care.** The results will be recorded for research purposes:

- Physical assessment of hindfoot/ankle, including vital signs
- X-rays of the hindfoot/ankle

The following procedures/assessment will be done solely for research purposes:

- Questionnaires
- Blood draw (1 ½ teaspoons) and analysis for Vitamin D levels (only at the 6 month visit)
- CT scan of your ankle/hindfoot
- At the conclusion of Visit #7, participation in the study is complete.
- 2. If this protocol involves study treatment, explain how a subject will be transitioned from study treatment when they have completed their participation in the study.

Example: If the subject will be taking an investigational drug, will they need to be put back on an approved drug when they have completed the study? If yes, explain how this will be accomplished and who will cover the cost. If the subject has a device implanted will it be removed? Again- who will cover the cost of the removal? **Instructions:** Answer NA if this study does not involve a study treatment.

Answer/Response: N/A.

Subject Compliance with Study Procedures

1. **Explain how the study team will monitor the subject for compliance with the study procedures.** (e.g. study team will administer study drug/ study interventions, study drug inventory of dispensed and returned drug, diary etc.)

Answer/Response: Study visits coincide with standard of care follow-up visits to their surgical procedure.

2. **Describe criteria for when a subject is considered to be non-compliant with study procedures.** (e.g. subject returns more than 20% of the study drug, subject misses 20% of study visits)

Answer/Response: Subject misses 30% of study visits

Bibliography

Version Date: 08/19/2021 Page Number: 9 of 10

- 3. K.L. Wapner. Triple arthrodesis in adults. J Am Acad Orthop Surg, 6 (1998), pp. 188–196

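### The primary comparison with history names no rate, source or historical count: 1 failure in 15 gives p = 0.027 against one CT-confirmed Background rate and p = 0.49 against the other

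*Combined protocol and SAP*

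**What the plan says.** The primary variable (Statistical Considerations, item 4) is fusion of more than 50% on CT. Item 2 gives the comparison: "We will compare primary outcome measures as a binary outcome using chisquare or Fisher exact analyses using existing failure rates as a historical control". The study has no control group (Study Design, item 1), so literature rates are the only comparator. The target is 15 patients (Human Participants, item 1).

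The Background offers several candidate rates and designates none:

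- For rhPDGF-BB and autograft, in that order: "arthrodesis rates, as confirmed on CT scan, were only 84% and 65% respectively".
- For ankle fusion: "recent literature has demonstrated that 10-40% of ankle fusions result in non-union".
- For triple arthrodesis: "published rates of non-union range from 0-10" per cent.
- For hindfoot fusion sparing the calcaneocuboid joint, a higher rate at the sponsor's own institution, with no figure.

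No number of patients accompanies any of these. The cohort mixes procedures: "Ankle arthrodesis, tibiotalocalcaneal arthrodesis, subtalar and triple arthrodesis procedures would be included in this cohort".

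The form's instructions for item 2 say that "the estimates and non-statistical assumptions of the statistical section should be supported by discussion in the background section", and that where testing is used the answer should "specify the null and alternative hypotheses, the test statistic, and the type I and II error rates". The answer gives no hypotheses and no error rates, and leaves the test statistic as an either/or.

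**The concern.** A test against history needs a benchmark fixed before the results are known. Here the benchmark is an unspecified plural, and the study is open-label, so whoever picks the rate may already know how many joints fused. Three further choices are open. A Fisher test or two-sample chi-square needs a historical count, and none is given. Nothing says which of the two tests applies. CT is listed at 3, 6 and 12 months (Study Procedures, Visits 5, 6 and 7), and the primary variable does not say which scan counts.

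At stake is the primary conclusion. With few failures, the same data could be reported as better than history or as no different from it. With a middling number, they could be reported as no different or as worse. The multivariate modelling mentioned in item 2 does not settle which rate is used.

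**Working it through.** There is no sample-size or power figure to reproduce: 15 is stated without a null rate, an alternative, an alpha or a power.

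**Inputs**

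- n = 15 (Human Participants, item 1).
- Historical failure rates from the two CT-confirmed fusion rates in the Background: 100 − 65 = 35% (autograft) and 100 − 84 = 16% (rhPDGF-BB).
- Assumed: two-sided 0.05. The failure counts are hypothetical.

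**Step 1. Each rate treated as fixed (one-sample exact binomial)**

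With X ~ Binomial(15, p0), the two-sided p-value sums the probabilities of all outcomes no more likely than the one observed. For 1 failure:

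- p0 = 0.35: Pr(X ≤ 1) = 0.65^15 + 15 × 0.35 × 0.65^14 = 0.0016 + 0.0126 = 0.0142. The upper tail, Pr(X ≥ 10), is 0.0124. Total p = 0.0266.
- p0 = 0.16: Pr(X ≤ 1) = 0.84^15 + 15 × 0.16 × 0.84^14 = 0.0731 + 0.2090 = 0.2821. The upper tail, Pr(X ≥ 4), is 0.2092. Total p = 0.4914 from unrounded values.

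All results:

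| Failures of 15 | p vs 35% | p vs 16% | Reading at 0.05 (35% / 16%) |
|---|---|---|---|
| 0 | 0.0020 | 0.1509 | better / no difference |
| 1 | 0.0266 | 0.4914 | better / no difference |
| 2 | 0.1039 | 1.00 | same |
| 3 | 0.2859 | 0.7213 | same |
| 4 | 0.5971 | 0.2824 | same |
| 5 | 1.00 | 0.0778 | same |
| 6 | 0.7877 | 0.0227 | no difference / worse |
| 7 | 0.4179 | 0.0052 | no difference / worse |
| 8 | 0.1750 | 0.0010 | no difference / worse |
| 9 | 0.0564 | 0.0001 | no difference / worse |
| 10 or more | ≤ 0.0140 | < 0.0001 | same (worse) |

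The verdict differs for 0, 1, 6, 7, 8 and 9 failures: six of 16 possible results. The low end is not remote. If the true failure rate were 16%, 0 or 1 failures would occur with probability 0.28 (the 0.2821 above).

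**Step 2. The planned type of test, with an assumed historical n of 100**

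| Failures of 15 | Fisher p vs 35/100 | Fisher p vs 16/100 |
|---|---|---|
| 1 | 0.035 | 0.70 |
| 6 | 0.78 | 0.039 |

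The same six results change verdict.

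**Step 3. Historical count and test, with the rate held at 35% and 1/15 observed**

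| Assumed history | Fisher | Chi-square, uncorrected | Chi-square, continuity-corrected | Smallest expected count |
|---|---|---|---|---|
| 7/20 | 0.10 | 0.048 | 0.12 | 3.4 |
| 21/60 | 0.053 | 0.031 | 0.066 | 4.4 |
| 35/100 | 0.035 | 0.027 | 0.056 | 4.7 |

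The smallest expected count is 15 × (total failures) / (total patients), for example 15 × 8 / 35 = 3.4. At an assumed 20 or 60, the choice between Fisher and uncorrected chi-square decides significance. Under Fisher, so does moving from 60 to 100.

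**The case against.** The strongest reply is that sensible choices are within reach. The two CT-confirmed rates come from one cited trial, so naming that trial and an arm would fix the count, and the sweep in Step 3 varies a number the sponsor could not then vary. Chi-square or Fisher is common shorthand for Fisher when expected counts are small, and every smallest expected count in Step 3 is below 5. The Background presents the graft as an alternative to autograft, which makes 35% the natural comparator. It also says "The purpose of this study is to examine 1-year outcomes", which points to the 12-month scan. The 16% rate belongs to a different product, and different verdicts against two comparators do not contradict each other. Finally, this is a 15-patient, single-arm, post-market study whose stated objective claims no superiority, and a historical p-value at that size carries little weight.

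Much of this is reasonable. The Step 3 figures illustrate what an unstated count can do and say nothing about the cited trial's actual size. The denominator problem would largely disappear once a source and arm were named. But the protocol names no source or arm, writes down no rule for the test, and ties the primary variable to no visit. The modest scope of the study argues for an estimate with an interval, not for leaving a planned test without a benchmark.

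**Conclusion.** The concern holds, and it must be fixed before CT results are examined. Following the plan as written, six of 16 possible results yield different primary conclusions depending on which of two CT-confirmed Background rates is used. No single result gives all three readings (better, no different, worse) against these two rates, and the observed fusion proportion does not depend on the choice.

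The size rests on n = 15, an assumed two-sided 0.05 level and hypothetical failure counts. The one-sample binomial is an illustration, not the planned test. Fisher reproduces the pattern, but only with a historical n of 100 that is assumed. The 1/15 reversal also holds one-sided (0.014 against 0.28) and by one-sample chi-square (0.021 against 0.32).

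One limit would survive the naming of a benchmark: even 0 failures in 15 gives p = 0.15 against 16%, so at this sample size no result could show fewer failures than that rate.

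**What to change.** 1. Make the primary result the proportion with more than 50% fusion on the 12-month CT, with an exact (Clopper-Pearson) 95% confidence interval, and list fusion by procedure type. By default, report the interval alone.
2. If a historical test is kept, name one CT-confirmed benchmark before CT results are seen, after checking at source that its CT timing, fusion threshold and procedures are comparable. Test it as a fixed rate with a two-sided exact binomial test at a stated alpha. Show the other CT-confirmed rate beside it without a second test.
3. If comparability cannot be confirmed, report the interval alone.
4. Do not test formally against the 10–40% or 0–10% ranges, whose method of ascertainment is not given.
5. State that a difference from the benchmark will not be attributed to the graft.

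A minimal repair that names one rate, source, count, test, visit and alpha would close the specification gap. The interval suits a study of 15 better.

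The cost is protocol wording. The sponsor gives up a free choice of comparator and reports a visibly wide interval: 14/15 fused is 93.3% (95% CI 68.1 to 99.8%), and 12/15 is 80.0% (51.9 to 95.7%).

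### The primary test is a two-group contingency test, but the study has one group and a comparator given only as percentages; for results near the threshold the verdict then depends on unstated choices.

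*Combined protocol and SAP*

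**What the plan says.** All references are to the combined protocol and SAP.

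- **Test.** Statistical Considerations, question 2: the primary outcome is treated as binary and compared "using chisquare or Fisher exact analyses using existing failure rates as a historical control". There is no rule for choosing between the two tests, no mention of a continuity correction, and no null hypothesis, alpha or sidedness, although the form asks for the hypotheses, test statistic and error rates.
- **Endpoint.** Statistical Considerations, question 4, names CT-confirmed arthrodesis with more than 50% fusion.
- **Design.** Study Design, question 2, describes a "post-market, prospective, non-randomized, PI initiated, open-label clinical evaluation of the implant". No control group is enrolled. The target is 15 subjects, with 18 to be enrolled.
- **Historical results.** The Background gives percentages only: "10-40% of ankle fusions result in non-union"; 0-10% non-union for triple arthrodesis; and, for a growth-factor product and autograft in one cited trial, "arthrodesis rates, as confirmed on CT scan, were only 84% and 65% respectively". No numerator or denominator appears, and none of these rates is named as the comparator.

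**The concern.** Fisher's exact test works on a two-by-two table of counts. The study fills one row; the other row has to come from somewhere, and the plan gives neither the source nor its size. If chi-square is instead read as a one-sample test against a fixed rate, no denominator is needed, but the pairing with Fisher then makes no sense and the approximation has few expected failures to rest on.

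This sentence is the whole inferential plan for the primary endpoint. If the historical denominator and the test are settled after the CT results are known, a borderline result could be called significant or not for reasons unrelated to the data.

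**Working it through.** **Inputs.** From the protocol: n=15 (target) and historical CT fusion of 65% or 84%, that is 35% or 16% failures; also the 10-40% and 0-10% non-union ranges. Assumed, because the protocol gives none: a two-sided 0.05 level and historical denominators m of 15 to 200.

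**The plan's own figure.** It states no power, alpha or threshold to reproduce. The only derivable number is enrolment: 15/0.9 = 16.7, so 17, which the planned 18 covers.

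**Expected failures, n × rate.** 15 × 0.10 = 1.5; 15 × 0.16 = 2.4; 15 × 0.35 = 5.25. At 0%, the bottom of the triple-arthrodesis range, the expected count is 0 and the one-sample statistic is undefined.

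**Same data, different denominators.** Take 14/15 fused against 65%, with the history entered as h/m. For m=15 the nearest whole count is 10/15, or 66.7%. The smallest expected count in each table is 15 × (1 + m − h)/(15 + m).

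| h/m | Smallest expected count | Fisher p | Pearson p |
|---|---|---|---|
| 10/15 | 3.0 | 0.169 | 0.068 |
| 13/20 | 3.4 | 0.101 | 0.048 |
| 26/40 | 4.1 | 0.045 | 0.036 |
| 39/60 | 4.4 | 0.054 | 0.031 |
| 65/100 | 4.7 | 0.035 | 0.027 |
| 130/200 | 4.95 | 0.024 | 0.024 |

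Fisher crosses 0.05 more than once as m grows. Fisher and Pearson disagree at m=20 and m=60. With a Yates correction, on which the plan is silent, m=40 gives 0.078 and m=100 gives 0.056, where both uncorrected Pearson and Fisher are below 0.05. The exact one-sample binomial test needs no m and gives p=0.027.

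**How far this reaches.** Over the same denominators, with Fisher and Pearson:

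- 11, 12 or 13 of 15 fused: every p exceeds 0.05 (lowest 0.086).
- 15/15 fused: every p is below 0.05 (highest 0.042).
- Against 84%: no favourable result reaches 0.05 by either test at the denominators tried. The exact test agrees: for 15/15, one-sided p = 0.84^15 = 0.073 and two-sided p = 0.151.

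**Size of the one-sample chi-square, nominal 5%, n=15.** The statistic is (x − nf)²/(nf(1 − f)), for x failures and rate f, compared with 3.84.

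- f=10%: x=4 gives (4 − 1.5)²/1.35 = 4.63, so the test rejects at 4 or more failures. True size is 5.6%, against 1.3% for the exact test. Zero failures gives 1.5²/1.35 = 1.67, so all the excess is in the unfavourable direction.
- f=16%: both tests have size 2.3%.
- f=35%: 5.6% against 2.7%; the favourable tail is 1.4% for both.
- f=30%, inside the ankle range: x=1 and x=8 both give 3.5²/3.15 = 3.89, so both reject, and size is 8.5%. The favourable part is 0.7^15 + 15 × 0.3 × 0.7^14 = 0.0047 + 0.0305 = 3.5%. The exact test rejects in that direction only at zero failures (0.5%).

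**The case against.** The best defence has four parts.

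**Counts may exist.** The historical rates cite publications, so a reader who infers that the control row would be made up goes beyond the documents. If a source reports counts, a two-sample exact comparison is legitimate and carries the benchmark's own sampling error, which a fixed-rate test ignores. This stands. What remains is that the protocol names neither the study nor its counts as the comparator.

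**No contradiction on controls.** A reader might set the answer No to "Will controls be used" against the historical control in the statistical section. The natural meaning of that answer is that no control group is enrolled, and a literature comparison is consistent with it.

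**A convention settles the test.** Using Fisher whenever an expected count is below 5 would send every table above to Fisher and remove the disagreements at 20 and 60. The plan does not state that convention, and Fisher alone still moves across 0.05 with m.

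**The reach is small.** It would be tempting to say that any result could be declared significant or not, or that chi-square generally inflates false claims of success. Neither is supported. Of the counts from 11 to 15, one changes verdict against 65%, and none of the favourable counts does against 84%. In many cells the chi-square and exact sizes are identical, and at 10% and 35% the excess lies only in the unfavourable tail. The 30% cell shows that nominal size is not reliably held, but it is not typical.

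**Conclusion.** The point holds as a mismatch between test and design. Fisher cannot be run from what the protocol supplies, chi-square rests on few expected failures, and nothing says which is used. In the cases examined, the consequence is confined to a result near the threshold: 14/15 against 65%, where p runs from 0.17 to 0.024 (Fisher) and from 0.068 to 0.024 (Pearson).

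These figures rest on assumed denominators of 15 to 200 and a two-sided 0.05 level. The choice of historical rate matters more than the denominator: 15/15 gives an exact two-sided p of 0.002 against 65% and 0.151 against 84%. Naming a better test without fixing the benchmark would therefore be an incomplete repair.

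**What to change.** In Statistical Considerations, question 2, replace the chi-square or Fisher wording with:

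- the proportion reaching more than 50% CT fusion, with a Clopper-Pearson 95% confidence interval;
- one exact one-sample binomial test against a single benchmark rate, with its source, alpha and sidedness fixed before results are seen.

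For illustration, 14/15 would be reported as 93.3% (95% CI 68.1% to 99.8%). Against 65% at one-sided 0.025, the rule would be at least 14/15, with exact alpha 15 × 0.35 × 0.65^14 + 0.65^15 = 0.0142 and power 0.549 if the true rate is 90%.

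If a two-sample comparison is preferred, name the source study with its numerator and denominator in advance and use one exact method only.

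The cost is a rewritten answer and no new data. The small downside is that a fixed-rate test ignores the benchmark's sampling error; giving the benchmark's own confidence interval, where its source reports counts, makes that visible. Rewording the controls answer under Study Design to mention a historical comparator is optional and not part of the defect.
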